4.5. Subjects for comparison

This study will include cigarette stores for comparisons with e-cigarette stores. For each e-cigarette store, one cigarette shop nearby will be conveniently selected for matching, because cigarettes are widely available in convenience stores, supermarkets, and tobacco and liquor shops, and thus these stores are impossible to systematically be pre-identified.

5. Study treatments

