5.1. Treatment and control

Each e-cigarette store will be visited by a simulated buyer (also serving the role of a data collector) who aged 18-19 years old and wear a certain type of attire, including carried accessories. If necessary, the buyers will claim that (1) they are adults but will not show any age proof; (2) they have never tried any tobacco products; (3) they want to buy e-cigarettes out of curiosity because their friends are using the products.

The sellers' behaviors and claims will be documented immediately after the simulated buyers leave the stores. The primary difference between the treatment group and control group is the attire that buyers wear: school uniforms vs. casual attire.

Treatment group: The e-cigarette stores will receive a simulated buyer of a randomly assigned sex who will wear a school uniform, carry a school bag, and attempt to purchase e-cigarette products.

Control group: The e-cigarette stores will receive a simulated buyer of a randomly assigned sex who will wear casual attire, carry a business style bag (backpacks for males and handbags for females), and attempt to purchase e-cigarette products.

1:1 matching: After mystery shopping and point-of-sale auditing in an e-cigarette store, simulated buyers will search for the nearest store where traditional cigarettes can be purchased and conduct a similar visit intervention.

Note: The simulated adolescent buyer (also the data collector) will role-play a minor under 18 years old who attempt to buy e-cigarettes. Only adolescents aged 18 or 19 years old will be recruited in this study because it is theoretically difficult to distinguish whether they are under or above 18 years old from the facial features. This trial will not recruit minors who are younger than 18 years old because it is illegal for them to purchase e-cigarette products in China.

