5.2. Treatment procedures

Before entering a store, the simulated buyers will observe and record the location and

exterior advertising from a hidden corner.

After that, the simulated buyers will enter the store and attempt to buy e-cigarette products. If the seller asks about their age, they will tell the seller that they are adults (18 years old or above) but will not show their ID cards or give any proofs to mimic the real-world situation. If the seller asks about buyer's smoking status, the buyer will claim that he/she has never tried any tobacco products including both e-cigarettes and cigarettes, and wants to buy e-cigarettes out of curiosity because his/her friends are using these products. The buyer will ultimately attempt to buy the cheapest e-cigarette product in the store for the budget reason, but he or she will not reveal this before asking about the price. To reduce potential biases caused by adolescent buyers' personalities and communication skills, a soft script will be developed to standardize the in-store interactions as much as possible (see Appendix 2).

After the assessment (approximately 10-15 minutes), simulated buyers will immediately leave the store and complete the rest of data entry to optimize retention. They will note the seller's responses during the visit, including whether or not inquiring about age, checking ID card, dissuading uses, and ultimately selling products. In addition, they will document the seller's demographic characteristics, marketing messages, interior decorations and signs. The detailed information about outcome measures is shown in Section 6. Data will be inputted via a self-developed instrument embedded in the online survey platform called Questionnaire Star accessed by smart phones.

After leaving the e-cigarette store, simulated buyers will search for the nearest cigarette shop and conduct a similar visit intervention. They will firstly observe the store's location and exterior advertising. Then, they will enter the shop and attempt to purchase a pack of cigarettes. If cigarette seller asks, they will answer that they are adults now and have never smoked. The adolescents will similarly record the behaviors and claims of the sellers in cigarette stores. The detailed information about outcome measures is shown in Section 6.

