7.6. Study visits and treatment procedures

The formal study will begin in July 2023. The simulated buyers and coordinators will be

divided into three teams, each including eight simulated buyers[†] (18-19 years old) and two coordinators (graduate students). Each team will travel from Beijing to all the metropolitan areas across mainland China (Appendix 8).

Simulated buyers will travel to new metropolitan areas by train or air and change into the prepared attire at the hotel (the type of attire worn on that day will be pre-determined by a random number). The team coordinator will then assign a list of pre-specified e-cigarette stores to each simulated buyer. Using the assistance of the AutoNavi Map, simulated buyers will travel by public transportation according to the geographic information on the list to the e-cigarette stores to conduct the survey. Each simulated buyer will visit 4-5 e-cigarette stores per day if possible.

The simulated buyers will take on the role of an adolescent who attempt to buy e-cigarette products, go into a store, talk to the seller, and try to make the purchase. They will record all the information using Questionnaire Star (an App) on their smart phone after the visit is completed. Upon the arrival, the simulated buyers will first observe the external environment of the store out of sight of the seller and fill in the related information. They will then enter the store, purchase e-cigarette products, and record seller responses and the internal environment of the store. After memorizing the information, they will leave the store, complete, and submit the data collection form online. The same simulated buyer will conduct a similar trial in one of the nearest cigarette stores, which serves as a match to the e-cigarette store that he or she just visited. After completing the visit, they will then travel to the next e-cigarette store. Survey details and measurements can be seen in **Section 5** and **Section 6**.

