Appendix 4 Assessing tool

E-cigarette store survey questionnaire

Basic Information

1. Survey date [Fill in the blanks] *-----Click to confirm

2. Simulated buyer's name [Fill in the blank] *-----Fill in the name

3. City where you are located [Fill in the blanks] *-----Please fill in "Beijing" in the format, do not fill in "Beijing City"

4. Store ID: _____ [fill in the blank] *----- Each store corresponds to an ID. Note that there may be e-cigarette stores very close to each other in practice, and the store names might not be easily distinguishable. Please check carefully.

5. Location of store: (automatically fill the building location by the GIS function embedded in the Questionnaire Star) [Fill in the blank] *

6. The simulated buyer's attire today [single-choice question] *

- Student uniform
- Casual attire

Outside Store Observation

7. Is it possible to study this store? *[Single choice question]

- Yes;

○No, unable to locate the store based on the geographic information. You can follow the map navigation to the building and walk around the area to try to find it. If you still cannot find it, contact the study coordinator to add a new store;

○No, possible danger in surroundings was perceived, such as remote alleys with no pedestrians at all;

○No, store closed upon arrival, even though it was confirmed to be in business before.
Note that some unopened stores can be observed, such as in pictures 1 and 2 below;

○No, other reasons _____ * (Please skip to the end of the questionnaire and submit your answer sheet).

8. The type of stores is [single choice question] *

○Open stores in shopping malls -----based on whether the counter can be accessed from the pedestrian area;

○Enclosed stores in shopping malls;

- Convenience store or small supermarket on the street — not primarily selling e-cigarettes;

- E-cigarette store with independent stores on the street

- E-cigarette store under an office building ----- [please note the distinction from an e-cigarette store that is an independent store on the street];

○Other type _____ *

9. Are any of the following places near the e-cigarette store (look around and within sight)?

[Multiple choice questions] *----- [Look around twice and mentally count 5 or more stores]

- School
- Shopping mall entrance, stairs-----This refers to the e-cigarette retail store in the mall
- Trendy toy store
- Beverage shop
- Female-only stores such as nail salons and cosmetics stores
- Internet cafe
- Bar
- Video arcade

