- Yes, the seller asked you (the simulated buyer) to leave after knowing that he or she did not have an ID card. (Please skip to the end of the questionnaire and submit your answer.)

In-store communication and records 2

24. Does the e-cigarette store sell the following types of e-cigarettes and accessories
[Multiple choice questions] **

Disposable e-cigarettes ----- Disposable e-cigarettes refer to those e-cigarettes that cannot be disassembled, refilled, or changed by the user and are thrown away after use. They can also be rechargeable. For example, the seller might describe them to you as "rechargeable for 1,000 puffs."

Reloadable e-cigarettes and/or cartridges ----- Reloadable e-cigarettes usually consist of two parts: a cigarette rod and a cigarette cartridge. The cigarette rod can be recharged and reused, while the cigarette cartridge is thrown away after use.

Open e-cigarettes that the user refills with e-liquid himself or herself ----- The e-liquid tank of open e-cigarettes is open and refillable. It can be refilled 3-6 times for continued use. The atomizer has a long service life.

Auxiliary accessories for e-cigarettes, such as protective cases, lanyards, etc.

Other, _____

25. Other items sold in the e-cigarette stores: [Multiple choice questions] *

No products other than e-cigarettes are sold

Power bank rentals

Addictive substances, such as tobacco, alcohol, and betel nut

Other _____

26. Did the seller proactively dissuade the simulated buyer from trying e-cigarettes? [Single Choice Question] * ----- The seller will tell you (the simulated buyer) that e-cigarettes are harmful, addictive, impossible to quit, don't try them, etc., in an attempt to discourage you from buying them.

Yes

No

27. The most popular flavor recommended to you (the simulated buyer) by the seller is [fill in the blank] * ----- Ask the seller, "With so many varieties, what are the differences?" and then, "Which one sells better?"

28. The second most popular flavor recommended to you (the simulated buyer) by the seller is [fill in the blank] * ----- If the seller only recommended one flavor in the previous question, you can fill in "none" for this question.

29. Is there a "Free Trial" sign or disposable filters in the store [Single-choice question] * -----Pay attention to whether there are disposable filters at the cashier]

Yes

No

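### The matched cigarette shop is chosen by three differing rules, and none excludes a shop already visited or a store in the e-cigarette sample

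*Protocol*

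**What the plan says.** Three different rules govern the choice of the cigarette shop.

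- **Nearest.** The Synopsis (Interventions) and Protocol 5.1 say that "simulated buyers will search for the nearest store where traditional cigarettes can be purchased". Protocol 5.2 agrees: "After leaving the e-cigarette store, simulated buyers will search for the nearest cigarette shop and conduct a similar visit intervention".
- **One of several.** Protocol 7.6: "The same simulated buyer will conduct a similar trial in one of the nearest cigarette stores, which serves as a match to the e-cigarette store".
- **Convenience.** Protocol 4.5: "For each e-cigarette store, one cigarette shop nearby will be conveniently selected for matching". SAP 2.1 repeats this in nearly the same terms.

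Safeguards against repeat visits exist only for e-cigarette stores. Protocol 4.4 has the coordinator make sure that a substitute e-cigarette store has not already been audited, and Protocol 7.2 keeps the pilot e-cigarette stores out of the main trial. No section sets a like condition for cigarette shops.

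The matched pairs serve the second of the secondary objectives (Protocol 2.3, SAP 1.2.2), which compares e-cigarette with cigarette retailers. They are analysed by McNemar's test (Protocol 8.5, SAP 2.3.5).

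**The concern.** The mystery-shopper method relies on a seller meeting an unknown customer. If two e-cigarette stores lead to the same cigarette shop, the second request comes to a seller who may remember the first. The answer may then reflect the earlier visit. Two pairs also share one shop, whereas McNemar's test treats every pair as independent.

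The convenience wording carries a different risk. The cigarette visit follows the e-cigarette visit, and buyers know both the attire and the e-cigarette result. A free choice of shop can therefore depend on that result.

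At stake is the validity of the paired comparison between the two store types.

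**Working it through.** The plan gives no overlap rate to reproduce, so the check has two parts: whether the text permits repeats, and how common they could be.

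**Step 1: can repeats occur under the text?**

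- Clusters are drawn by location and public transport. They usually hold 4 stores (Protocol 7.1.3) or about 5 (SAP 1.1.2), and each goes to one buyer.
- That buyer visits 4-5 e-cigarette stores a day, each followed by a cigarette shop (Protocol 7.6), in the one attire drawn for that day (Protocol 7.1.3).
- The assessing tool warns: "Note that there may be e-cigarette stores very close to each other in practice". The warning is about entering the right store ID, but it shows that such closeness is expected.
- A team of eight buyers (nine in one team) works a city together (Protocol 7.6), so buyers from adjoining clusters can also reach the same shop.
- No condition bars a used shop. A strict nearest rule would require the repeat whenever two stores have the same nearest shop.

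Repeats are therefore possible. The looser wordings allow a buyer to avoid one but do not require it.

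**Step 2: how often?**

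An illustration under assumptions: m e-cigarette stores and K cigarette shops are placed uniformly at random in one cluster area, and each store is matched to its nearest shop (10,000 simulated clusters per setting). If the m stores use u distinct shops, the repeat share is (m − u)/m, averaged over clusters. Multiplying by about 1,080 matched visits gives the last column.

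| K (assumed) | m = 4 | m = 5 | Repeats among 1,080 |
|---|---|---|---|
| 10 | 17.5% | 22.1% | 189-239 |
| 20 | 9.2% | 11.9% | 99-129 |
| 40 | 4.8% | 6.3% | 52-68 |
| 80 | 2.3% | 3.2% | 25-35 |
| 160 | 1.1% | 1.6% | 12-17 |

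For example, 1,080 × 0.175 = 189 and 1,080 × 0.221 ≈ 239. With only 5 shops in the area the shares would be 30.8% and 37.7%. The documents give no shop density, so they do not single out any row. The model leaves out sharing between buyers, which would raise the shares. It also assumes strict adherence to the nearest rule, and the looser wordings could lower them.

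**Step 3: what could this do to the comparison?**

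If a share f of cigarette visits are repeats, carry-over can move the cigarette-store rate by at most f, and only if every repeat changes its result in the same direction. At f = 1.1% the ceiling is 1.1 percentage points; at f = 22.1% it is 22.1 points. The actual shift is some unknown fraction of that, possibly none. The loss of independence remains even if no result changes.

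**The case against.** The strongest reply is that cigarettes are widely available (Protocol 4.5 says so itself), that stores are sampled at random across a city's main districts, and that repeats would then be rare. This stands as an argument for the lower rows of the table. It does not supply the missing rule.

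It is also fair to say that a buyer cannot be both bound to the nearest shop and free to choose. Carry-over and selective choice are alternatives, and which one applies depends on the wording a buyer follows. On selective choice, pay is a flat daily sum (Protocol 7.3), so the documents show no incentive to favour lenient shops. They show only that the choice is open and made with knowledge of the earlier result.

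Four stronger readings are tempting, and the documents do not support them.

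- **The buyer is sent back into the e-cigarette store just left.** A reader might infer this because the assessing tool lists convenience stores as a store type and, among other goods sold, "Addictive substances, such as tobacco, alcohol, and betel nut". But Protocol 4.5, 5.2 and 7.6 most naturally describe a separate shop, and Protocol 7.1.1 removes outlets judged not to be e-cigarette shops. An explicit exclusion is still worth adding.
- **The paired difference shifts by several points.** No overlap rate or carry-over effect is given, so no such figure can be derived.
- **The attire comparison among cigarette stores is biased.** Attire is randomised, and nothing in the documents shows carry-over differing by attire.
- **The cigarette form lacks a location field.** Appendix 4 reproduces only the e-cigarette form, so this cannot be established.

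**Conclusion.** The concern holds as a gap in the selection rule. The wordings disagree, and none of them excludes a shop already visited or a store in the e-cigarette sample. The same seller may be approached twice, the second result may be affected by the first, and pairs that share a shop are not independent. The convenience wording also leaves an unblinded buyer free to choose after the e-cigarette result is known.

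The frequency is unknown. The range of about 1-22% of matches rests on the assumed geometry, on 10 to 160 cigarette shops per cluster area and on strict use of the nearest rule.

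The exposure is mainly the secondary comparison of store types. The primary attire outcome would be touched only if a sampled e-cigarette store served as another store's cigarette match before its own visit. The documents do not exclude that, but nothing suggests it would be common. This is an inexpensive improvement to a secondary analysis and does not challenge the main result.

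**What to change.** Put one rule in the Synopsis, Protocol 4.5, 5.1, 5.2 and 7.6, and SAP 2.1. The match is the nearest cigarette shop that:

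1. is not the matched e-cigarette store;
2. is not on the city's e-cigarette list or among its replacements; and
3. has not already been visited by any buyer in the trial.

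If the nearest shop fails a condition, take the next nearest. Remove the convenience wording.

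Buyers check a shared list of visited shops on their phones and call the coordinator only when in doubt. Appendix 8 assigns each city to a single team, so a list per city is enough. The shops need not be identified in advance, which Protocol 4.5 says cannot be done. Record an ID and location for each cigarette shop, and report the number of repeats with the paired analysis.

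The cost is a sentence in each place, a shared list, and an ID and location entry if the cigarette form does not already have them. The downside is that a few matches will lie slightly further from their e-cigarette store.

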5.2. Treatment procedures

Before entering a store, the simulated buyers will observe and record the location and

exterior advertising from a hidden corner.

After that, the simulated buyers will enter the store and attempt to buy e-cigarette products. If the seller asks about their age, they will tell the seller that they are adults (18 years old or above) but will not show their ID cards or give any proofs to mimic the real-world situation. If the seller asks about buyer's smoking status, the buyer will claim that he/she has never tried any tobacco products including both e-cigarettes and cigarettes, and wants to buy e-cigarettes out of curiosity because his/her friends are using these products. The buyer will ultimately attempt to buy the cheapest e-cigarette product in the store for the budget reason, but he or she will not reveal this before asking about the price. To reduce potential biases caused by adolescent buyers' personalities and communication skills, a soft script will be developed to standardize the in-store interactions as much as possible (see Appendix 2).

After the assessment (approximately 10-15 minutes), simulated buyers will immediately leave the store and complete the rest of data entry to optimize retention. They will note the seller's responses during the visit, including whether or not inquiring about age, checking ID card, dissuading uses, and ultimately selling products. In addition, they will document the seller's demographic characteristics, marketing messages, interior decorations and signs. The detailed information about outcome measures is shown in Section 6. Data will be inputted via a self-developed instrument embedded in the online survey platform called Questionnaire Star accessed by smart phones.

After leaving the e-cigarette store, simulated buyers will search for the nearest cigarette shop and conduct a similar visit intervention. They will firstly observe the store's location and exterior advertising. Then, they will enter the shop and attempt to purchase a pack of cigarettes. If cigarette seller asks, they will answer that they are adults now and have never smoked. The adolescents will similarly record the behaviors and claims of the sellers in cigarette stores. The detailed information about outcome measures is shown in Section 6.

5.3. Design and selection of the uniforms

In 2015, China's Ministry of Education, together with multiple departments including the National Standardization Committee, issued a directive titled 'Opinions on Further Strengthening the Management of School Uniforms for Primary and Secondary School

Students'.¹⁶ The policy, although not legally mandated, encourages students to wear school uniforms on weekdays. The decision on school uniforms is jointly made by the schools and committees of students' parents. However, once established in a school, it in reality becomes mandatory for all students to adhere to. Due to the fact that wearing school uniforms by secondary school students has become a social consensus, those wearing uniforms are naturally perceived as minors in China, especially when he/she looks young.

This study chooses school uniforms and casual attire as the indicator of being potential minors and adult buyers, respectively. The school uniform chosen is the most common style of middle/high schools in China, as the study will be conducted in thirty-six major metropolitan areas across mainland China. The casual attire style chosen is the most commonly seen in China. Appendix 3 shows pictures for adolescent models with pre-selected school uniforms and casual attire.

The same styles of school uniforms and casual attire with corresponding accessories, including school bags (adolescents), backpacks (male adults), and handbags (female adults), will be ordered and provided to simulated buyers free of charge.

6. Outcome Measures

6.1. Primary outcome measure

The primary outcome is the sales of e-cigarettes to simulated buyers, as adolescents successfully purchase e-cigarette products from the stores without showing any age proof.

